3 SAMPLE SIZE DETERMINATION

A sample size of 12 study participants per group yields approximately 95% power to detect a difference in the percent reduction from baseline in creatine kinase between the active and placebo groups using a Wilcoxon rank sum test at the two-sided 0.05 type 1 error rate.

The power calculations assume that the percent reduction in creatine kinase in the active dose group is approximately normally distributed with a mean of 80% and a standard deviation of 8%; that 4 of the placebo patients will have a percent reduction similar to the active dose group; and the remaining 8 placebo patients will have a percent reduction that is normally distributed with a mean of 10% and a standard deviation of 8% (Mammen and Timakou 2015).

4 POPULATIONS FOR ANALYSIS

- **Enrolled Set (ES):** will include in all screened participants including screen failures.
- **Intention-to-Treat Population (ITT):** will include all randomized participants.
- **ITT_{NoCOVID-19}:** will include all ITT participants excluding those with confirmed COVID-19 as observed during any visit of the Main Portion of the study and reported in the AE eCRF form.

Of note, ITT_{NoCOVID-19} will be considered in any analysis specified in the current document during the Main Portion only, provided it differs by at least 15% from the ITT in terms of number of participants.

- **Per Protocol Set (PPS):** will include all participants in the ITT Population who have completed the 8 Week Treatment Period and have no important protocol deviations. Important protocol deviations will be evaluated during ongoing data cleaning meetings prior to unblinding of the data.

If a participant received multiple doses of different study drug (i.e., placebo and 0.3 mg/kg), the patient will be assigned to the dose group which they received at the highest frequency within the Main Portion of the study.

- **Intention to Treat - Extension (ITT_{EXT}):** will include all participants who entered the Extension Portion of the study.
- **Safety Set (SS):** will include all participants who received at least 1 dose of study drug during the Main Portion of the study irrespective if they continued to the Extension Portion. Participants will be analyzed based on the actual treatment received.

If a study participant received multiple doses of different study drug (i.e., placebo and 0.3 mg/kg), the participant will be assigned to the dose group which he/she received at the highest frequency within the Main Portion of the study.

Of note, participants who were on placebo during the Main Portion of the study and continued to the Extension Portion will be included in both groups depending on the study period assessed. Safety results on 0.3 mg/kg across the Main and Extension Portions will be combined.

- **Safety Set No Covid-19 (SSNOCOVID-19):** will include all participants in the SS except those with confirmed COVID-19 (as reported in AE eCRF form) during any time of the study (Main or Extension Portion).
Of note, SSNOCOVID-19 will be considered in any analysis specified in the current document, provided it differs by at least 15% from the ITT in terms of number of participants.
- **Pharmacokinetic Per-Protocol Set (PK-PPS):** will include those study participants in the SS who received 1 dose, had at least 1 valid PK measurement post first dose of study treatment, and no important protocol deviations affecting the PK variable, as confirmed during a pre-analysis review of the data prior to database lock.
- **Pharmacodynamic Per-Protocol Set (PD-PPS):** will include those study participants in the SS who received 1 dose, had at least 1 valid PD measurement post first dose of study treatment, and no important protocol deviations affecting the PD variable, as confirmed during a pre-analysis review of the data prior to database lock.

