8.3 SELECTION CRITERIA FOR THE EXTENSION PORTION

1. Completion of the Main Portion of the study.
2. Continues to meet inclusion criteria 2, 11, and 12 from the Main Portion of the study.
 2. *Able to provide informed consent, including signing and dating the ICF.*
 11. *Female subjects of childbearing potential must have a negative serum pregnancy test at Screening and a negative urine pregnancy test within 24 hours prior to the first dose of study drug.*
 12. *Sexually active female subjects of childbearing potential (i.e., women who are not postmenopausal or who have not had a hysterectomy, bilateral oophorectomy, or bilateral tubal ligation) and all male subjects (who have not been surgically sterilized by vasectomy) must agree to use effective contraception during the study. Postmenopausal women are, for the purposes of this protocol, defined as women who have gone 12 consecutive months without menstruation.*

3. Did not start any disallowed medication per the exclusion criteria from the Main Portion of the study or alter the dose of any other concomitant medication, unless medically indicated.
4. Is able and willing to comply with the requirements of the study.
5. Does not have any new medical condition (since entry into the Main Portion) or any other reason that, in the opinion of the investigator or Sponsor, would disqualify the subject from participation in the Extension Portion of the study.

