5.6.2 Adverse Events

Adverse events will be captured from the time of informed consent signature (only the SAEs) or from the time of first administration (Treatment Emergent Adverse Events) and will be reported if occurred during scheduled or unscheduled visits. As Treatment Emergent AE (TEAE) is defined as an AE starting on or after the time of first administration of study drug or an AE that increases in severity after treatment start, if the event was present at the time of the treatment initiation. Reporting of TEAEs refer to the period until the administration of the last study dose plus 40 days (or last visit depending which occurs first).

AEs will be classified according to the Common Terminology Criteria for Adverse Events (CTCAE) Version 5.0 for severity. For any AE where it is not possible to provide a CTCAE grading, the event will be assessed using a standard intensity classification (mild, moderate and severe). For the purpose of the tabulations all CTCAE severity classifications will be mapped to a mild/moderate/severe grade as described below:

- Grade 1 - Mild
- Grade 2 - Moderate
- Grade 3, 4, 5 - Severe

These will be tabulated together with the AEs that were not classified according to CTCAE criteria i.e., all Grade 1 AEs as per CTCAE criteria will be included in the ‘mild’ category together with those AEs classified as mild as per the ‘standard’ intensity classification.

If a particular AE severity is missing, then this will be listed as missing and treated as missing in summaries. If a participant has experienced more than one TEAE within the same PT, then the AE with the greatest severity will be presented. If a participant reported more than one AE within the same (System Organ Class) SOC then the participant will be counted only once with the greatest severity at the SOC where applicable.

Where dates are missing or partially missing, AEs will be assumed to be treatment-emergent unless evidence exists that does not allow the AE to be treatment-emergent. Handling of missing dates for classification of AEs as TEAEs is described in Section 5.1.1.8.

TEAE summaries will be performed in SS and repeated in SS_{NOCOVID-19} if at least 15% of the participants have at least one AE as ‘Confirmed COVID-19’.

Summaries may also be repeated in SS among participants with at least one TEAT based on the COVID-19 period defined as:

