- Before the pandemic: a TEAE will be assigned to this period if the start date of the event is on or after the date of the first administration of study drug on Day 1 but before the cut-off date of 11th MAR 2020.
- During/after the pandemic: a TEAE will be assigned to the during/after the pandemic Period if the start date of the event is on or after the date of the first administration of study drug on Day 1 but after the cut-off date of 11th MAR 2020.

A TEAE will be counted as related to study drug if the response to the question “Relationship to Study Medication” is “Related”. Severe TEAEs are those with CTCAE Grade 3 or above, or those without a CTCAE grading classified as ‘severe’ by the Investigator. If a participant reports the same event with different relationship assessments, then participant will be counted under both related and not related categories.

Adverse events will be presented as “number of participants (percentage of participants) [number of events]”. In this style of output, “[number of events]” will include all cases of an AE including repeat occurrences in individual participants, while “number of participants” will count each participant only once.

TEAE Summaries will be reported separately within the Main Portion and within the Main and Extension Portion of the study and presented by primary system organ class (PSOC) and preferred term (PT) within each IMP. PSOCs will be sorted alphabetically. PTs will be sorted by decreasing frequency of Zilucoplan within each PSOC; ties will be sorted alphabetically within Zilucoplan. TEAEs will be mapped to a study portion based on the onset date.

The following summaries will be produced:

- TEAE overview table in SS and SS_{NOCOVID-19}, displaying participants with at least one TEAE, with at least one TEAE before/after 11th March 2020, with at least one serious TEAE, with at least one TEAE resulting to permanent withdrawal from study medication, with at least one drug-related TEAE and with at least one TEAE leading to death
- TEAEs by PSOC and PT, in SS
- TEAEs by PSOC and PT by COVID-19 period, in SS
- Serious TEAEs by PSOC and PT in SS
- Serious TEAEs by PSOC and PT for each COVID-19 period, in SS
- TEAEs by PSOC, PT and maximum CTCAE V5.0 Grade, in SS
- TEAEs by PSOC, PT and maximum relationship, in SS
- Serious TEAEs by PSOC, PT and maximum relationship, in SS
- Fatal TEAEs by PSOC, PT and maximum relationship, in SS

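### The no-COVID Safety Set excludes for COVID-19 at any time in the study, so the supplementary Main Portion no-COVID TEAE tables can lose completers because of infections after Week 8 (minor)

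*SAP*

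**What the plan says.** SAP Section 4 defines two no-COVID sets with different windows. The efficacy set, ITT NoCOVID-19, takes the ITT "excluding those with confirmed COVID-19 as observed during any visit of the Main Portion of the study" and is used for Main Portion analyses only. The safety set, SS NoCOVID-19, takes all Safety Set (SS) participants "except those with confirmed COVID-19 (as reported in AE eCRF form) during any time of the study (Main or Extension Portion"). Its scope is wide: "SSNOCOVID-19 will be considered in any analysis specified in the current document, provided it differs by at least 15% from the ITT" in number of participants.

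SAP 5.6.2 states the condition differently. TEAE summaries are run in the SS and repeated in SS NoCOVID-19 "if at least 15% of the participants have at least one AE as" confirmed COVID-19, with no portion of the study named. The same section says "TEAE Summaries will be reported separately within the Main Portion and within the Main and Extension Portion of the study". Its list of outputs names the TEAE overview table for both the SS and SS NoCOVID-19. That table has rows for TEAEs leading to permanent withdrawal of study medication and to death.

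On who can reach the Extension, the first selection criterion in Protocol 8.3 is "Completion of the Main Portion of the study". Protocol 7.1 and SAP 1.2 both bar anyone who permanently stops study drug before Week 8. Under Protocol 7.2 the Extension is open-ended outside France and lasts 18 months in France.

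**The concern.** The Main Portion TEAE tables are the only placebo-controlled safety comparison in the study, and they cover 8 weeks. As SS NoCOVID-19 is written, membership of the no-COVID version of those tables depends on what happens to a participant after the 8 weeks. Someone infected well into the Extension disappears from them, although nothing in that person's Main Portion data was touched by COVID-19.

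The loss is also selective. A participant who stopped treatment before Week 8 never enters the Extension and cannot be removed for an Extension infection; a completer can. A table meant to show Main Portion safety without COVID-19 would then differ from the full table partly because completers had been taken out. A reader could take that difference for an effect of COVID-19.

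**Working it through.** **The plan's own figure.** The only number the SAP gives here is 15%. With 24 planned participants, 0.15 × 24 = 3.6, so 4 are needed (4/24 = 16.7%; 3/24 = 12.5% falls short). The sample size calculation plays no part.

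**Which infections count for an 8-week table?**

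| | ITT NoCOVID-19 | SS NoCOVID-19 |
|---|---|---|
| Infection in Main Portion | excluded | excluded |
| Infection in Extension only | kept | excluded |
| Tables covered | Main Portion only | any analysis |

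Four Extension infections and none in the Main Portion would leave ITT NoCOVID-19 identical to the ITT, while SS NoCOVID-19 loses 4 and its trigger is met.

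**Can Extension infections meet the trigger alone?** The documents give no COVID-19 risk, so these are assumptions. Let m be the Main Portion risk and e the further risk in the Extension, with all completers entering the Extension. A completer is excluded with probability p = m + (1 − m)e. With 24 completers, the chance of meeting the trigger is P(X ≥ 4) for X ~ Binomial(24, p). With 21 completers, X is the sum of Binomial(21, p) and Binomial(3, m). For m = 3%:

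| e | p | Expected exclusions (24 completers) | Of which Extension only, 24(1 − m)e | P(X ≥ 4), 24 completers | P(X ≥ 4), 21 completers |
|---|---|---|---|---|---|
| 0% | 3.0% | 0.72 | 0 | 0.5% | 0.5% |
| 5% | 7.85% | 1.88 | 1.16 | 11.5% | 9.1% |
| 10% | 12.7% | 3.05 | 2.33 | 36.4% | 29.4% |
| 20% | 22.4% | 5.38 | 4.66 | 81.9% | 73.9% |
| 30% | 32.1% | 7.70 | 6.98 | 97.3% | 94.5% |

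With 24 completers and m varied from 1% to 5%, the e = 10% result ranges from 26.2% to 46.7% and the e = 20% result from 76.6% to 86.2%. From Main Portion infections alone the chance is 0.01%, 0.5% and 3.0% for m = 1%, 3% and 5%.

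**Effect on one percentage.** Assume 2 of 12 in an arm stop before Week 8 for an AE, and 4 completers across the trial are later excluded for Extension infections. The numerator stays at 2. The result depends on how many of the 4 come from that arm:

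- none: 2/12 = 16.7%
- one: 2/11 = 18.2%
- two: 2/10 = 20.0%
- three: 2/9 = 22.2%
- four: 2/8 = 25.0%

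**The two triggers.** Section 4 compares SS NoCOVID-19 with the ITT; 5.6.2 counts participants with a confirmed COVID-19 AE. Suppose 24 are randomized, 22 dosed and 2 of those infected. SS NoCOVID-19 then has 20, which differs from the ITT by 4/24 = 16.7%, so Section 4 runs the repeat. Section 5.6.2 gives 2/22 = 9.1% and does not. The rules diverge only if someone is randomized but not dosed, which should be rare because both are scheduled for Day 1.

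**The case against.** The strongest reply is that this is a conditional, descriptive repeat and nothing rests on it. That largely stands. SAP 5.1 runs safety primarily in the SS, 5.6.4 bases laboratory, vital sign and ECG analyses on the SS, and no hypothesis test uses SS NoCOVID-19. COVID-19 is also visible elsewhere in 5.6.2: TEAEs by pandemic period, a flag in the AE listings, and a separate listing of confirmed cases. The any-time rule may have been written with the combined Main and Extension tables in mind. If so, the SAP does not say it; "SSNOCOVID-19 will be considered in any analysis specified in the current document" covers the Main Portion tables too.

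Four stronger readings are tempting, and the documents do not support them.

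- A reader might infer that the planned 8-week safety tables lose participants. They do not; only the no-COVID repeats can.
- A reader might infer that Extension event rates are computed on a set short of long-term users. SAP 5.6.2 and 5.6.3 list the exposure-adjusted tables in the SS. The general wording would at most add repeats beside them.
- A reader might infer that discontinuation percentages are inflated by construction. Exclusions for Main Portion infections, or for COVID-19 in an early discontinuer's 40-day follow-up, can also remove numerator cases. An AE that starts in the Main Portion but ends treatment in the Extension belongs to a completer. Only for AEs that stopped treatment before Week 8, and only for exclusions due to Extension infections, is the numerator protected.
- A reader might infer that the Main Portion no-COVID table will change after the Week 8 lock. Protocol 12.2.1 describes that lock, but no text says the Main Portion safety tables are re-run later. They could change if they were.

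**Conclusion.** The point holds, and it is minor. As written, SS NoCOVID-19 lets post-Week 8 infections decide who appears in the supplementary 8-week no-COVID TEAE tables, and those infections can remove only Main Portion completers. The parallel ITT NoCOVID-19 definition in the same section shows that the SAP already has the narrower rule available.

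The issue arises only if the trigger is reached, which takes 4 of 24. Extension infections count toward it and, at the assumed risks, would be the main way of reaching it. The text alone establishes the mechanism; its size rests on COVID-19 risks that the documents do not supply. Nor can the direction of any between-arm bias be established: everyone in the Extension receives zilucoplan, and the asymmetry is between completers and early discontinuers, not between arms.

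The trigger mismatch is a wording matter with practical effect only if some randomized participants are never dosed.

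**What to change.** In SAP Section 4, for Main Portion tables, define SS NoCOVID-19 by confirmed COVID-19 with onset in the Main Portion, as ITT NoCOVID-19 already does, and apply the 15% trigger to that count. The number lost from 8-week tables because of Extension-only infections then becomes 0.

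Replace the condition "provided it differs by at least 15% from the ITT in terms of number of participants" with one measured against the SS, and state that same single trigger in 5.6.2.

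For any combined Main and Extension repeats, state how COVID-19 is handled. Any-time exclusion and censoring at onset answer different questions, and the choice is the sponsor's.

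The cost is a few lines of SAP text and a small programming change. TEAEs are already mapped to study portion by onset date in 5.6.2, so no new data are needed.

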5 STATISTICAL ANALYSES

5.1 General Considerations

- Descriptive statistics for continuous endpoints will include number of participants with available measurements (n), mean, standard deviation (SD), median, 25% and 75% percentiles, minimum and maximum. Confidence Intervals (CIs) will be provided where appropriate. In general, all study endpoints will be summarized descriptively by IMP and overall (if applicable).
- Frequencies and percentages will be presented by IMP for categorical and ordinal variables. Unless otherwise noted, the denominator for percentages will be based on the number of participants included in the respective analysis set.

Participants with missing data can generally be accounted for using the following approaches:

- For summaries of demographics and baseline characteristics: summarize percentages based on all participants in the analysis set and include a “Missing” category (corresponding to participants with missing data for the variable being summarized) as the last row in the list of categories being summarized. Percentages are associated with the missing row so that percentages sum to 100.
- For summaries of efficacy and safety variables, unless otherwise specified: summarize percentages based only on those participants with observed data for the variable being summarized. As the denominator may be different from the number of participants in the

analysis set being considered, the denominator should be displayed in the table. The general format for displaying this will be “n/Nsub (%).”

All percentages will be displayed with one decimal place. No percentage will be displayed for zero counts and no decimals will be presented when the percentage is 100%. If there are no missing data for a variable, then the missing row can be removed for that variable in the shell. If there are no observations in any specific eCRF-specified category, then retain that row and present 0's across the table. E.g., if there are no 'American Indian/Alaskan native' participants in the study but this was one of the Racial Group categories in the eCRF, then retain the row and populate it with 0 values.

Decimal places for descriptive statistics will always apply the following rules:

- “n” will be an integer;
- Mean, SD, and percentiles will use one additional decimal place compared to the original data reported;
- CV [%] will be presented with one decimal place;
- Minimum and maximum will have the same number of decimal places as the original value reported.

Derived variables in general will be displayed to 1 more decimal place than the variables used in the derivation. If the number of decimal places reported in the raw data is varied, then either the maximum raw number of reported decimal places or 3 will be used, whichever is the lowest.

If no participants have data at a given time point, for example, then only n=0 will be presented. However, if n<3, present the n, minimum and maximum only. If n=3, n, mean, median, minimum and maximum will be presented only. The other descriptive statistics will be left blank.

If for a particular output there are no valid cases to summarize for any variable, then report “No data observed”.

Demographics and baseline characteristics will be analyzed in ITT. Separate tables based on the enrollment date relative to 11 Mar 2020 will be created.

Efficacy analyses will be performed primarily in the ITT population. Prior and Concomitant medications summaries will be performed in the SS. Medical History will be analyzed in the ITT. Safety, PK and PD analyses will be performed primarily in the SS, PK-PPS and PD-PPS.

Comparative efficacy analysis (inferential statistics) will focus on the Main Portion of the study only where both active and placebo treatments are given in blinded manner.

Baseline is defined in Section [5.1.1.2.4](#).

Change from Baseline is defined as: post baseline value - baseline value.

Percentage Change from Baseline is defined as: $100 \times (\text{Change from Baseline}/\text{Baseline})$, if baseline is greater than zero.

IEs are defined as these events that may preclude an observation from the study or affect the interpretation of the results; in the current setting the following is considered as IE:

- Intake of medication which is prohibited by the protocol (complement inhibitor, rituximab, statins, or any investigational medicinal product while on study)

Since the primary analysis of the primary and secondary endpoints will be based on treatment policy estimand (that is, observed case analysis) the only data manipulation to be considered is the censoring of efficacy values following to the administration of any prohibited medication.

5.1.1 General study level definitions

5.1.1.1 Analysis visit windows

All data will be analyzed based on the visits identified per the schedule of activities in protocol. Mapping to analysis visit windows will not be applied, except for end of treatment (EDV) visits (specified in Section 5.1.1.2.3).

5.1.1.2 Analysis Time Points

5.1.1.2.1 Relative day

- For days on or after the day of first dose of study drug and prior to or on the day of last study drug dose (e.g., the day of 1st dose will be Day 1) the relative day will be calculated as:
- For days after the last dose of study drug, the relative day will be calculated as:
- For days prior to the 1st dose of study drug, the relative day will be calculated as:
- Relative day will not be calculated for partial dates and it must be left blank in these instances.

There is no relative Day 0. Relative day is not calculated for partial dates in cases where relative day is shown in a participant data listing. In such cases, relative day should be presented as ‘--’ in the participant data listings.

